## 17.2. Analysis of Outcomes

### 17.2.1. Primary Outcome

The percentage of patients that died by the end of day 14 will be presented for each group. Risk of death will be modelled using logistic regressionf,10, with treatment group fitted as a covariate, and ideally adjusting for the key confounders: age, sex, and number of comorbidities at baseline. The odds-ratio comparing RDV with controls, estimated from the model, will be presented together with a 95% CI and a p-value.

Note on adjustment for confounders: the number of covariates that may be added to the model depends on the number of deaths recorded (rule of thumb, 10 events per covariate fitted). Clinical trials data indicate that 14-day mortality for RDV in this type of patient may be around 3.1%, meaning that if we include 500 RDV-treated patients, we might expect 16 deaths from that group. Under the assumption that the risk of death is not lower in the control group, this suggests at least 32 deaths (under 1:1 matching), and so we project that there will be sufficient power to enable adjustment for 3 confounders given the higher expected matching ratio.

---

f Stuart (2010) recommends that in the analysis of cohorts matched using propensity scoring, it is more common to simply pool all the matches into matched treated and control groups and run analyses using the groups as a whole, rather than using the individual matched pairs.

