### 17.2.2.3. Time-to-death

We restrict this analysis to deaths within 28 days of baseline. Any patient alive at the end of the study period will be censored at 28 days. Any patient lost to follow-up prior to 28 days will be censored at their last known follow-up. This outcome will be analysed as a time-to-event using the methodology described in 17.2.2.1 above.

### 17.2.2.4. Clinical status at day 15

Clinical status is defined as an 8-point ordinal score with the following categories: (1) Not hospitalised, and not limited physically; (2) Not hospitalised, but limited physically and/or requiring supplementary oxygen; (3) Hospitalised but medically OK; (4) Hospitalised, not requiring supplementary oxygen, but needs on-going COVID related care; (5) Hospitalised and requiring supplementary oxygen; (6) Hospitalised and requiring non-invasive ventilation; (7) Hospitalised and requiring mechanical ventilation or ECMO; (8) Dead. See Appendix A1.1 below for a definition of how this outcome is derived. Where day 15 CRFs are unavailable, we will look at all available adjacent CRFs to estimate a

---

g We have used the same definition for this outcome as was used in the ACTT-1 trial.

most likely clinical status. In cases where there is ambiguity over likely clinical status, and independent statistical reviewer, blind to all but the clinical status CRF data, will adjudicate likely status. If it is not possible to estimate the outcome, the outcome will be treated as missing.

The outcome will be analysed using a proportional odds model with treatment arm and disease severity as covariates, and adjusting for key confounders: age, sex, and number of comorbidities at baseline. The treatment odds ratio estimated from the model will be presented along with a 95% CI and a p-value.

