6	Hospitalised, on non-invasive ventilation or high flow oxygen devices	
DAILY TREATMENT CRF (day 15):
 
 
• Non-invasive respiratory support = YES
 
OR
 
• High-flow nasal cannula = YES
 
 
AND
 
 
• Invasive respiratory support = NO
 
• ECMO = NO
 
 
OR
 
 
• FiO2 >0.4, or FiO2 >40%
 

		
OR
 
 
• O2 flow > 4 L/min
 

7	Hospitalised, on mechanical ventilation or ECMO	
DAILY TREATMENT CRF (day 15):
 
 
• Invasive respiratory support =YES
 
 
OR
 
 
• ECMO = YES
 

8	Death	
OUTCOME CRF (dated day 15 or less):
 
 
• Death= YES
 

NA	Unable to classify	If death before day 15, lost to follow-up prior to day 15, or due to incomplete CRF completion

\* If use of supplemental oxygen is unknown or missing, use either (1) DAILY CRF: recorded “Oxygen saturation” SpO2 lowest % is  $\geq 94\%$ ; or (2) DAILY CRF: recorded “Oxygen saturation” SpO2 lowest % is  $\geq 88\%$  plus: Admission CRF co-morbidities “Chronic pulmonary disease” is “Yes”.

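### Appendix Table 1 codes a death before day 15 both as score 8 and as unclassifiable, with no rule on which applies

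*SAP*

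**What the plan says.** SAP section 17.2.2.4 defines an eight-point ordinal score whose top categories are "7) Hospitalised and requiring mechanical ventilation or ECMO; (8) Dead". No time limit is put on the death category. For the derivation the section points to the appendix: "See Appendix A1.1 below for a definition of how this outcome is derived". Table 1 in the Appendix is therefore the programming specification.

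Table 1 has two entries that concern death:

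- Row 8 requires the Outcome CRF to record death and to fall in the window "OUTCOME CRF (dated day 15 or less".
- The NA row, labelled as unable to classify, applies "If death before day 15, lost to follow-up prior to day 15, or due to incomplete CRF completion".

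On outcomes that cannot be derived, section 17.2.2.4 says: "If it is not possible to estimate the outcome, the outcome will be treated as missing". On the model it says: "The outcome will be analysed using a proportional odds model with treatment arm and disease severity as covariates", with further adjustment for age, sex and number of comorbidities.

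For the primary outcome, section 17.2.1 says: "The percentage of patients that died by the end of day 14 will be presented for each group".

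**The concern.** Two adjacent rows of one table give opposite codings to the same patients. A programmer who follows the NA row literally is following the SAP, and so is one who follows row 8.

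The choice matters because death is the worst category. Setting early deaths to missing would condition the comparison on survival to day 15, which is a post-treatment event. The comparability that the propensity matching is meant to create would no longer hold among the patients left in the model. Section 9.2 marks this outcome as one defined in ACTT-1, and section 11 says that outcomes were chosen for direct comparison with that trial and SOLIDARITY. A score that omits most deaths would not match the eight-category definition in section 17.2.2.4. Section 18 puts accounting for types of missingness out of scope, so no planned analysis of this outcome would bring the deaths back.

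**Working it through.** **1. The two rows by day of death**

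| Day of death | Row 8 | NA row | Result |
|---|---|---|---|
| 0 to 14 | score 8 | unclassifiable | conflict |
| 15 | score 8 | does not apply | score 8 |
| after 15 | does not apply | does not apply | scored on day-15 status |

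Counting days from the same baseline in both places, death before day 15 is the same set as death by the end of day 14. The conflict therefore covers every primary-outcome death.

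**2. How many patients**

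Inputs from section 17.2.1: 14-day mortality of 3.1% with RDV, 500 RDV patients, control risk not lower. Section 10 gives a matching ratio from 1:1 to 1:4.

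- RDV deaths: 500 × 0.031 = 15.5, rounded up to 16. This reproduces the SAP's figure.
- Total at 1:1: 2 × 15.5 = 31.0, or 2 × 16 = 32 with each group rounded up first. The SAP states at least 32.
- Total at 1:2, 1:3 and 1:4, if controls also have 3.1%: 15.5 × 3 = 46.5, 15.5 × 4 = 62, 15.5 × 5 = 77.5.

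Under the NA row all of these become missing. Under row 8 all stay in the model as score 8.

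**3. Effect on the odds ratio**

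The SAP gives no distribution of the score, so one is assumed for controls (scores 1 to 8): 0.40, 0.20, 0.05, 0.08, 0.10, 0.05, 0.058, 0.062. The death share of 6.2% is 2 × 3.1%. A proportional odds model is fitted to the expected proportions with equal group sizes, first with deaths as score 8, then with deaths removed. An odds ratio above 1 means better status with RDV.

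| Assumed RDV effect | Deaths as 8 | Deaths as NA |
|---|---|---|
| Uniform odds ratio 1.50 on all categories | 1.50 | 1.47 |
| Uniform odds ratio 1.25 | 1.25 | 1.23 |
| Uniform odds ratio 0.67 | 0.67 | 0.69 |
| Deaths halved to 3.1%, survivors' distribution unchanged | 1.11 | 1.00 |
| Deaths doubled to 12.4%, survivors' distribution unchanged | 0.82 | 1.00 |

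A second assumed distribution for survivors (scores 1 to 7: 0.45, 0.20, 0.05, 0.06, 0.12, 0.07, 0.05), with 3.1% deaths on RDV and an effect on death alone, gives 1.00, 1.11, 1.23 and 1.36 with deaths kept when control mortality is 3.1%, 6.2%, 9.3% and 12.4%. With deaths removed it gives 1.00 throughout. With a uniform odds ratio of 1.50 and control mortality of 5% to 12%, removing deaths gives 1.48 to 1.44.

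**4. Scale against sampling error**

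On the first distribution with 500 per group, the standard error of the log odds ratio is about 0.114.

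- Deaths halved: ln(1.106) = 0.101, and 0.101 / 0.114 ≈ 0.9 standard errors.
- Deaths doubled: ln(0.819) = −0.200, and 0.200 / 0.114 ≈ 1.8 standard errors.

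**The case against.** The best defence is that the SAP, read as a whole, intends to keep early deaths. Section 17.2.2.4 has a death category without a date limit. Row 8 reaches back before day 15, and that reach would have no use if earlier deaths were unclassifiable. Missing status is reserved for outcomes that cannot be estimated, and a recorded death is known. The NA row then looks like a drafting slip in a fallback category. This is persuasive on intent, but the document nowhere says so, and the NA row names early death explicitly. The contradiction stands.

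Two stronger readings are tempting and are not supported.

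- A reader might infer that the plan drops deaths from this analysis. It does so only if the NA row is applied over row 8, and nothing in the SAP says that it is.
- A reader might infer that a mortality harm or benefit would be hidden from the study. It would not. The primary outcome, 28-day mortality and time-to-death are defined separately and do not use Table 1, so every death by day 14 is counted there under either coding.

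The size also needs care. In the examples where RDV acts on death alone, the odds ratio of 1.00 follows by construction, because survivors were assumed identical. Such a pattern also departs from the proportional odds assumption of the planned model. Under a uniform odds ratio, the distortion is small.

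**Conclusion.** Table 1 is wrong as written: it assigns deaths on days 0 to 14 to two incompatible codes, and no other section resolves the conflict. This is an internal inconsistency, not a deliberate choice to exclude deaths.

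If the NA row prevails, only deaths on day 15 itself keep score 8, and the treatment comparison is restricted to patients alive at the end of day 14. The resulting bias ranges from slight, when RDV shifts all categories alike, to loss of the whole effect, when RDV changes mortality only. That range rests on assumed score distributions. The count of deaths rests on the SAP's own 3.1% and 500 patients.

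The reach is secondary outcome 4 of 10, and the primary conclusion cannot change. The point is a should-fix.

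**What to change.** In Appendix Table 1, delete the clause on death before day 15 from the NA row. Add a sentence that any death on or before day 15 is score 8. Keep NA only for patients whose status at day 15 is truly unknown, through loss to follow-up or incomplete CRFs.

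The cost is one line of SAP text and an entry in the Change Control table. No data collection, sample size or model changes. It should be settled before the score is programmed, so that the coding is not chosen with the data in view.

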### 6.1. EAMS Background

The MHRA EAMS (Early Access to Medicine Scheme) is a form of compassionate use programme. EAMS aims to give patients with life threatening or seriously debilitating conditions access to medicines that do not yet have a marketing authorisation when there is a clear unmet medical need. The scheme is voluntary and operates within the current regulatory structure. The MHRA requires that a Registry be utilised to support capture of the real-world outcomes of the use of an EAMS medicine in UK patients. Data captured through an EAMS are expected to be used to support cost effectiveness and commissioning discussions as the medicine is licensed and becomes available for routine clinical use in the UK.

The Deputy Chief Medical Officer (DCMO) for Her Majesty's Government has mandated that data on all patients that receive Remdesivir through the EAMS must be captured through the ISARIC 4C Clinical Characterisation Protocol UK (CCP-UK) case report forms (CRFs), as coordinated by the COVID-19 Clinical Information Network (CO-CIN). Completion of the mandatory fields of the ISARIC WHO CCP-UK CRFs is required, to support ongoing implementation, including determination of future drug allocations between NHS hospitals, and evaluation ([link to forms](#)).

The DCMO has commissioned an analysis of efficacy and safety based on the pragmatic data being collected by CO-CIN.

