## Appendix

Table 1: Clinical status ordinal score at day 15 mapped to ISARIC data fields

Score	Clinical Status	ISARIC v9.3 Data Field(s)
1	Not hospitalised, and no limitations on activities	
OUTCOME CRF (if dated day 15 or less):
 
 
• Discharged alive expected to survive = YES
 
AND
 
• Ability to self-care at discharge = ‘Same as before illness’ OR ‘Better’
 
AND
 
• Oxygen therapy?* = NO
 
 
OR
 
 
• Hospitalisation= YES
 
AND
 
• Medically fit for discharge = YES
 

2	Not hospitalised, limitation on activities and/or requiring home oxygen	
OUTCOME CRF (if dated day 15 or less):
 
 
• Discharged alive expected to survive = YES
 
AND
 
• Ability to self-care at discharge = ‘Worse’
 
OR
 
• Oxygen therapy? = YES
 

3	Hospitalised, not requiring supplemental oxygen – no longer requiring ongoing COVID related medical care	
OUTCOME CRF (dated day 15 or less):
 
 
• Hospitalisation= YES
 
 
AND
 
 
• Ongoing health care needs NOT related to COVID = ‘YES’
 

4	Hospitalised, not requiring supplemental oxygen, requiring on-going COVID related care	
DAILY TREATMENT CRF (day 15):
 
 
• Any supplemental oxygen = NO
 
• Non-invasive respiratory support = NO
 
• Invasive respiratory support = NO
 
• Non-invasive ventilation = NO
 
• High-flow nasal cannula = NO
 
• ECMO = NO
 

5	Hospitalised, requiring supplemental oxygen	
DAILY TREATMENT CRF (day 15):
 
 
• Any supplemental oxygen = YES
 
• Non-invasive respiratory support = NO
 
• Invasive respiratory support = NO
 
• High-flow nasal cannula = NO
 
• ECMO = NO
 

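### Day-15 status: Table 1 has no score for a known live discharge, off oxygen, whose self-care item is blank, and its score 1 rule does not measure the score 1 label

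*SAP*

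**What the plan says.** Clinical status at day 15 is a secondary outcome (SAP 9.2, item 4). It is scored on an 8-point scale and analysed with a proportional odds model (SAP 17.2.2.4). Appendix Table 1 maps the scale to CRF fields.

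- **Score 1** is labelled "Not hospitalised, and no limitations on activities" in Table 1 and "Not hospitalised, and not limited physically" in 17.2.2.4. The data rule needs an Outcome CRF dated day 15 or less, discharge alive, oxygen NO, and self-care recorded as "Same as before illness’ OR ‘Better". A second branch admits patients still in hospital but medically fit for discharge.
- **Score 2** needs discharge alive with self-care *Worse* or oxygen YES.
- **Score 8** needs death recorded on an Outcome CRF dated day 15 or less.
- **Row NA** applies to deaths before day 15 and to patients "lost to follow-up prior to day 15, or due to incomplete CRF completion".
- **The footnote** gives an SpO2-based substitute when oxygen use is unknown or missing. It gives none for self-care.

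Section 17.2.2.4 adds two steps before a value is lost. Adjacent CRFs are consulted when day-15 CRFs are unavailable, and ambiguous cases go to an independent statistical reviewer who sees only the clinical status CRF data. After that: "If it is not possible to estimate the outcome, the outcome will be treated as missing".

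**The concern.** Two things look wrong at the good end of the scale.

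First, a patient may be known to be alive and out of hospital by day 15, and so in one of the two best categories, yet have no score because one form item is blank. The authors foresaw item-level gaps, since they wrote a substitute for oxygen, but they left self-care uncovered. Table 1 points to NA and 17.2.2.4 points to adjudication, so two analysts could treat the same record differently. If such records are lost, information is thrown away; if they are lost at different rates in the two groups, the treatment odds ratio is biased.

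Second, the label of score 1 describes an absolute state while the field records change from the pre-illness state. SAP 9.2 says that the cohort includes some long-term institutionalised patients, so discharges of people who were dependent before COVID-19 and are unchanged should be expected. They would be reported as having no limitations. Nothing in such a record is missing or ambiguous, so the steps in 17.2.2.4 do not reach it.

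**Working it through.** The SAP states no rate, power or sample size for this outcome, so there is no figure of its own to reproduce. The check has two parts.

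**1. Applying Table 1 to a patient discharged alive by day 15.** Score 2 is read as discharged and (self-care *Worse* or oxygen YES).

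| Self-care | Oxygen NO | Oxygen YES | Oxygen missing |
|---|---|---|---|
| Better | 1 | 2 | footnote rule |
| Same | 1 | 2 | footnote rule |
| Worse | 2 | 2 | 2 |
| Blank | **no score: NA or adjudication** | 2 | footnote rule; if that gives NO, **still no score** |

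The gap is therefore specific: blank self-care with oxygen NO, whether recorded or inferred. The adjacent-CRF step does not obviously close it. It is worded for unavailable CRFs, whereas here the Outcome CRF exists with one item blank, and self-care at discharge is named only under the Outcome CRF. The adjudicator has no other stated source for it.

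The row *Same*, oxygen NO always gives score 1, whatever the level of dependence before illness.

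**2. What losing such records does to the odds ratio.** All rates here are assumptions. Take the same true distribution over scores 1 to 8 in both groups, 45/20/5/5/8/4/3/10%, so the true odds ratio is 1.00 and 65% are discharged. Delete a share of scores 1 and 2 only: 10% in the RDV group and 20% in controls.

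- Discharged, retained: RDV 0.65 × 0.90 = 0.585; control 0.65 × 0.80 = 0.520.
- Total retained: RDV 0.585 + 0.35 = 0.935; control 0.520 + 0.35 = 0.870.
- Odds ratio (worse status) at the cut between discharged and not discharged: (0.35/0.585) / (0.35/0.520) = 0.80/0.90 = 0.89.
- At the cut between alive and dead: (0.10/0.835) / (0.10/0.770) = 0.92.
- At the cut between score 1 and the rest: (0.530/0.405) / (0.510/0.360) = 0.92.

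The proportional odds fit averages over the cuts:

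| Blank among scores 1–2, RDV / control | Fitted OR for worse status (truth 1.00) |
|---|---|
| 10% / 10% | 1.00 |
| 5% / 15% | 0.92 |
| 10% / 20% | 0.91 |
| 10% / 30% | 0.82 |
| 20% / 10% | 1.10 |

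Under a second assumed distribution (70% discharged, 18% inpatient, 12% dead), 10% / 20% gives 0.92 and 10% / 30% gives 0.83. If blanks differ by group but fall equally on all eight scores, the fitted odds ratio is 1.00. With scores 1 and 2 combined, no discharge is deleted and 1.00 is recovered.

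**The case against.** The strongest reply is that the SAP does not condemn these records. A patient who must be either 1 or 2 is an ambiguous case, 17.2.2.4 sends ambiguous cases to a blinded reviewer, and missing is the last resort. This stands in part. A reader might infer from Table 1 alone that every discharge with blank self-care is lost. That is not so: with oxygen YES the score is 2, and otherwise adjudication may prevent the loss. What remains is that no rule is fixed, and that the reviewer would choose between 1 and 2 without the item that separates them.

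A reader might also infer that the scheme selectively drops good outcomes. The SAP does not show this. The same NA row lists deaths before day 15, the worst category. Scores 4 and 5 depend on several items of a day-15 daily form, so incomplete forms can remove middle categories too.

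Nor does the SAP establish that completeness differs by group. Section 6.1 says that government "mandated that data on all patients that receive Remdesivir through the EAMS must be captured", and no equivalent is stated for controls. But the mandate concerns mandatory fields, and self-care is not shown to be one of them. EAMS status ended in July 2020, while data collection runs to the end of November. Section 8.4.2 excludes patients in either group who lack the Day 1 daily form or the Medication section of the Outcome CRF. Unequal completeness is possible, not demonstrated.

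Finally, SAP 11 wants direct comparison with ACTT-1, and combining two levels shortens the scale. That is a fair cost, and the reason to keep the 8-level model alongside. Whether the 1/2 boundary matches that trial's cannot be judged here, because the SAP does not reproduce the trial's scale.

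**Conclusion.** The point holds in a limited form. Table 1 has no rule for a known live discharge, off oxygen, with self-care blank, and its default is NA although the score can only be 1 or 2. Independently of any missing data, the score 1 rule measures change from before illness while its label claims absence of limitation.

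The certain costs are lost or guessed values and a mislabelled category. Bias in the odds ratio is conditional: it needs blanks that differ by group and are concentrated in scores 1 and 2. Under those assumptions, a difference of 10 percentage points moves a true 1.00 to about 0.91 or 0.92 when controls have more blanks, and to about 1.10 when the RDV group has more. With equal rates there is no bias. A reader should not conclude that the result is tilted towards RDV, because the SAP supports neither a rate nor a direction.

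This is one of ten secondary outcomes. The change should be made because it is cheap, but the primary analysis is untouched.

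**What to change.** 1. State in Table 1 and in 17.2.2.4 that no patient with *Discharged alive expected to survive* = YES, dated day 15 or less, is classed NA because self-care or oxygen is blank.
2. Fit the main proportional odds model with scores 1 and 2 combined as one level, *Discharged alive* (7 levels). This uses only recorded facts and removes the mislabelled boundary from the model.
3. Report the 8-level model as a sensitivity analysis, in which discharged patients enter only if self-care is recorded. Give the number of blanks by group beside it.
4. Relabel the 1/2 split as self-care the same as or better than before illness, versus worse and/or home oxygen.
5. In the same edit, reconcile two further conflicts in Table 1. The NA row lists death before day 15, which score 8 already covers. The second branch of score 1 admits patients still in hospital but medically fit for discharge, which contradicts the label of score 1 and overlaps score 3. Without this, combining scores 1 and 2 would leave those inpatients in the wrong level or in none.

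The cost is SAP wording, one recode and one extra model fit. The main model loses one scale level and a little precision.

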##### 8.4.1. Inclusion criteria

- Laboratory confirmed SARS-CoV-2 infection
- Hospitalised
- Aged  $\geq 18$  yearsa at baseline
- Requiring supplementary oxygen ( $SpO_2 \leq 94\%$ ) at any time during 24 hours post baseline
- RDV initiated  $\leq 24$  hours post baseline (RDV group only)b

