##### 8.4.2. Exclusion criteria

- Requiring a high flow cannula, any ventilation or ECMO during first 24 hours post baselinec
- Pregnant
- Chronic kidney disease
- RDV initiated  $> 24$  hours post baselined
- Is a COVID-19 re-admission (was previously hospitalised for COVID-19)
- Missing Day 1 Daily Treatment CRF
- Missing ‘Medication’ section of the Outcome CRF

---

a RDV was recommended in people aged 12 and over, and weighing over 40kg. Weight was not generally measured at baseline for practical reasons, so we have excluded children aged 12-17 in order to be sure that no-one in the control group was likely to weigh less than 40kg.

b This criteria is an ideal, to measure the effectiveness of RDV initiated close to baseline. If RDV is more routinely given later than this, we will either remove this criteria, or move the window of inclusion to say 3 days. Statistics describing when RDV treatment was initiated compared with baseline, will be presented.

c This subgroup will be analysed separately (see Section 19).

d See footnote b above.

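### When oxygen use is missing, the day-15 score infers 'no oxygen' from SpO2 without requiring room air, only towards the best category, with cut-offs that overlap the entry criterion

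*SAP*

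**What the plan says.** **Entry (SAP Section 8.4.1).** The cohort is limited to patients "Requiring supplementary oxygen" within 24 hours of baseline, with SpO2 of 94% or below in brackets after those words. The criterion does not mention room air. It does not say whether the bracket defines oxygen need, adds a condition or illustrates it. Section 8.4.2 separately excludes patients with "Missing Day 1 Daily Treatment CRF".

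**Day-15 clinical status (Section 17.2.2.4 and Appendix, Table 1).** One route to score 1, the best category, has three conditions: discharge alive, ability to self-care unchanged or improved, and "Oxygen therapy?* = NO". The asterisk leads to the footnote: "If use of supplemental oxygen is unknown or missing, use either (1) DAILY CRF: recorded “Oxygen saturation” SpO2 lowest % is" 94% or above. The alternative is 88% or above "plus: Admission CRF co-morbidities “Chronic pulmonary disease” is “Yes". Neither limb refers to room air, FiO2 or oxygen flow, and the footnote does not say which day's form to use.

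**Other rows.** Score 2 can be reached through a positive oxygen-therapy field, which has no asterisk. Scores 4 and 5 use a recorded Daily CRF field, for example "Any supplemental oxygen = YES" for score 5, also without an asterisk. Table 1 has a row for patients who cannot be classified, which covers incomplete forms.

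**The concern.** Saturation alone does not show whether a patient is receiving oxygen. A reading of 96% may mean healthy lungs or effective oxygen. The footnote treats both as no oxygen, so where the field is blank it can place a patient discharged on oxygen in the best category because the oxygen is working. The substitution also works in one direction: a missing field can be resolved to NO, never to YES.

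The cut-offs also conflict with the entry criterion. The same reading can signify oxygen need at entry and absence of oxygen in the footnote.

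Two things are at stake. The first is the accuracy of one secondary outcome, the ordinal score at day 15. The second is reproducibility of the cohort. Section 8.4.1 feeds every analysis, and two programmers could code its bracket differently.

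**Working it through.** The SAP gives no figure that depends on this point, so there is nothing to reproduce. The check sets the two rules side by side and then follows a patient through Table 1.

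**1. Overlap of the cut-offs**

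- Entry rule, taking the bracket as written: SpO2 ≤ 94 means oxygen needed.
- Footnote rule: SpO2 ≥ 94, or SpO2 ≥ 88 with chronic pulmonary disease, means no oxygen.

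Applying both to whole-number values from 70% to 100%:

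| Patient | Values meeting both rules | Count |
|---|---|---|
| No chronic pulmonary disease | 94 | 1 |
| Chronic pulmonary disease | 88, 89, 90, 91, 92, 93, 94 | 7 |

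No value falls under neither rule.

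**2. A discharged patient with the oxygen field missing and self-care unchanged**

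- Without the footnote, score 1 needs NO and score 2 needs either worse self-care or YES. Neither is met, so the patient is unclassifiable.
- With the footnote and a lowest SpO2 of 96% on oxygen, the field is taken as NO and the patient gets score 1. The true category is 2 if oxygen continues at home.
- With the footnote and a lowest SpO2 of 92% without chronic pulmonary disease, the footnote does not apply. Nothing turns the missing field into YES, so the patient remains unclassifiable.

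The footnote can therefore add patients to score 1 but never to score 2.

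**3. Which outcomes are touched**

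- Clinical status at day 15: yes, through score 1 only.
- Time to recovery (Section 17.2.2.1): no. It depends on discharge or the end of COVID-related care.
- 14-day mortality (Section 9.1), 28-day mortality and time to death: no.

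**4. Size**

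The share of discharged patients wrongly moved from score 2 to score 1 is m × h × s × c, where:

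- m is the share with oxygen use missing;
- h is the share of those going home on oxygen;
- s is the share of those whose lowest SpO2 meets the footnote;
- c is the share of those with unchanged or better self-care.

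The SAP gives none of these. Purely as an illustration, assume m = 20%, h = 5–15%, s = 60–80%, and c at its maximum of 1:

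- low: 0.20 × 0.05 × 0.60 × 1 = 0.006, or 0.6%;
- high: 0.20 × 0.15 × 0.80 × 1 = 0.024, or 2.4%.

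Any c below 1 lowers both figures. The range shows the order of magnitude under stated assumptions and is not an estimate for this study.

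**5. Entry**

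Take a patient whose every reading in the first 24 hours is above 94% while on oxygen. If the bracket is coded as the whole test, this patient is left out. If recorded oxygen is the test, the patient is in. Take a patient with a reading of 94% or below who is given no oxygen. The first coding lets this patient in and the second may not. The SAP does not say which coding applies.

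**The case against.** The footnote is a fallback, not the general rule for being off oxygen at day 15. With the oxygen field completed, the problem cannot arise. Even when the footnote applies, score 1 by this route needs discharge alive and unchanged or better self-care. A reader might infer that a patient can be counted as recovered with no change in saturation. The SAP does not support that: an unchanged reading alone gives nobody score 1, and the outcome called recovery does not use SpO2. This objection stands and limits the point.

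A reader might also infer that the wrong patients enter the study. That follows only if the bracket in Section 8.4.1 is the whole test. The criterion also speaks of requiring oxygen, and it looks at any time in 24 hours. A patient corrected by oxygen is lost only if no reading in that window, including before oxygen started, was 94% or below. The required Day 1 Daily CRF fits oxygen need being read from that form. This stands too: the defect is ambiguity, not a demonstrated wrong cohort.

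Different cut-offs at acute admission and at discharge need not be a contradiction. The CRF is not at hand, so its SpO2 field might specify room air. Section 17.2.2.4 provides for adjacent forms, a blinded reviewer and a missing category. The rule is the same in both groups, and CPD is a propensity-score covariate (Section 8.7). No differential bias has been shown.

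These arguments reduce the consequences but do not remove the defect. The SAP states neither a room-air condition nor a reason for the different cut-offs. Because the footnote gives a definite answer, a patient it classifies need not appear ambiguous and so may never reach the reviewer. Balancing chronic pulmonary disease between groups does not correct a wrong score.

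**Conclusion.** The point holds in a limited form. For missing oxygen data, the footnote uses saturation without a room-air condition to assign NO, and it can only move patients towards the best score. Its cut-offs overlap the entry bracket at 94% for everyone and at 88–94% in chronic pulmonary disease.

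The direct effect is confined to one secondary outcome: misplacement in score 1 rather than 2, or rather than unclassifiable, among discharged patients with unchanged or better self-care. It is probably small. Its size cannot be computed, because the SAP gives neither the rate of missing oxygen data nor the distribution of SpO2; the 0.6–2.4% above rests wholly on assumed inputs.

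The entry bracket has wider reach because it helps define the cohort for every analysis, including 14-day mortality. What can be said there is only that the cohort may differ with how the bracket is coded. The SAP supports no figure for that effect and no direction of bias.

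**What to change.** **Table 1 footnote.** Infer no oxygen first from the oxygen fields of the last available Daily CRF: supplemental oxygen recorded as NO, or FiO2 and O2 flow showing none given. Use SpO2 only if it was recorded on room air. Otherwise treat the score as missing, as Section 17.2.2.4 and the unclassifiable row already allow, and add a sensitivity analysis that assigns these patients score 2.

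**Section 8.4.1.** Derive oxygen need from the recorded supplemental oxygen field on the Day 1 Daily CRF, which Section 8.4.2 already requires. State whether the SpO2 bracket is an alternative room-air criterion.

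**Both places.** Reconcile the entry and footnote cut-offs, or state why they differ. No separate entry rule for chronic pulmonary disease is needed to resolve this point.

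**Cost.** SAP wording and a revised derivation, using fields that Table 1 already names. The downside is a few more missing day-15 scores.
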